
Fidelity & Adaptation

Main Question:

To what extent are intervention local authorities adhering to the intended systemic practice pilot model?

Methods

Intervention group:

- Keyworker survey
- Family interviews
- Keyworker interviews and focus groups
- Systemic practitioner analysis of case files
- Observations of training and practice
- Keyworker and systemic practitioner case studies and learning log
- Administrative data on families and keyworkers

Dosage & Quality

Main Questions:

- How much of the systemic practice pilot model has been delivered?
- How well are different components delivered in each local authority?

Methods

Intervention group:

- Keyworker survey
- Family interviews
- Keyworker interviews and focus groups
- Systemic practitioner analysis of case files
- Observations of training and practice
- Keyworker and systemic practitioner case studies and learning log
- Administrative data on families and keyworkers

Reach & Responsiveness

Main Questions:

- What is the rate of participation by practitioners in the training?
- What is the extent of practitioners' engagement in the systemic practice model?
- What is the extent of engagement from families' keyworkers?

Methods

Intervention group:

- Keyworker survey
- Family interviews
- Keyworker interviews and focus groups
- Systemic practitioner analysis of case files
- Observations of training and practice
- Keyworker and systemic practitioner case studies and learning log
- Administrative data on families and keyworkers

Acceptability

Main Question:

Is the systemic practice pilot model acceptable to practitioners and families?

Methods

Intervention group:

- Keyworker survey
- Family interviews
- Keyworker interviews and focus groups
- Systemic practitioner analysis of case files
- Observations of training and practice
- Keyworker and systemic practitioner case studies and learning log

Programme Differentiation

Main Question:

To what extent is the systemic practice pilot model different from existing practices?

Methods

Intervention group:

- Keyworker survey
- Family interviews

- Keyworker interviews and focus groups
- Systemic practitioner analysis of case files
- Observations of training and practice
- Keyworker and systemic practitioner case studies and learning log
- Administrative data on families and keyworkers

Control group:

- Keyworker survey
- Administrative data on families and keyworkers

Mechanisms

Main Question:

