2. Focus groups and interviews with keyworkers (including systemic champions), the local authority systemic practitioners and senior staff (service leads and team managers).
3. Interviews with families receiving early help support
4. Administrative data collection from IFT and local authorities looking at training, implementation of systemic practice and support to families.
5. Observations of training, group reflective practice sessions, and (if feasible) keyworker sessions with families. Action learning research through analysis of keyworker and systemic practitioner case studies and learning logs.
6. If feasible, analysis of keyworker casefiles by embedded local authority Systemic Practitioners

In control local authorities the IPE will include:

1. Surveys of keyworkers at the start of the pilot and at the end.
2. Focus groups with keyworkers and interviews with senior staff (service leads and team managers)
3. Administrative data collection about business as usual implementation of key worker practice.

Practitioner surveys

For both the impact and IPE evaluation design a short online surveys of keyworkers will be administered to the intervention and control group keyworkers (as shown in the table below) led by Ecorys. The survey will be used in intervention areas to understand keyworker perspectives on implementation and fidelity to the systemic practice pilot. This will include training, use of the systemic practice virtual hub, support from the local authority systemic practice lead and systemic champions as well as the use of systemic practices (such as group reflective supervision) and tools (such as genograms). In addition to the perceived impact of the pilot on keyworkers and on families. In the control

arm the survey will be used to understand business-as-usual including standard practice and training. The survey will also be used to capture practitioner information such as roles and qualification levels as well as practitioners outcome measures for the pilot RCT.

Table 11: Survey timings

| | Baseline survey Administered before training session 1 | Post-training survey Administered at the final training session | Endline survey At the end of the pilot |
|------------------------|--|---|--|
| Intervention LA | X | X | X |
| Control LA | X | - | X |

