A key part of the IPE will be understanding whether practice has changes as a result of the training and support. Observing practice through analysis of keyworker casefiles could be a way of assessing change. We will assess the feasibility of analysing keyworker case files to assess the implementation, use and quality of systemic practice by keyworkers. We will work with intervention area systemic practitioners and team managers to assess whether it is feasible in terms of capacity and capability of. We will develop a short assessment criteria to assess the use and quality of systemic practice drawing on the Systemic Therapy Inventory of Change (STIC) and the Systemic Practice Competency Scale (SPCS). We request each intervention area provide three randomly selected cases from families who closed to the service just before the pilot began and three files from cases who closed in the latter stages of the pilot (estimated between December 2025 and February 2026). These cases will be anonymised and only information pertaining to practice and processes provided. The evaluation team will then use the assessment criteria to code and analyse case files to understand if there has been changes to practice in terms of systemic practice principles, terms or tools used

Monitoring and administrative data

Administrative data from intervention and control local authorities will be collected to understand contextual service and team factors alongside implementation and fidelity of the practice model. As set out in *Compliance and Fidelity* above, this will include data on:

- Training attendance (from IFT and local authorities);
- Implementation of systemic practice such as number of systemic practice group reflective sessions and genograms created (from intervention local authorities);
- Keyworker caseloads, number of family assessments and closure forms; and
- Children and young people and parents/carers keyworker support (see impact evaluation data collection for more information).
- Usage of the Virtual Systemic Practice Hub such number and type of resources used and use of the Q&A and other forums

Analysis

Our analytical approach will involve a structured and robust process of data collation, sorting, coding and tagging (data preparation) and thematic investigation against the evaluation questions (data analysis). An overview of the methods can be found in below.

Practitioner Survey

- Data Collection Methods: Online pre-, post-, and end-line survey

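### The protocol names two different assessors for the case-file analysis; under one of them, the staff who deliver the model would judge whether practice changed

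*Protocol*

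**What the plan says.** The Protocol assigns the case-file work in three places.

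- **IPE research methods, intervention local authorities, item 6:** "If feasible, analysis of keyworker casefiles by embedded local authority Systemic Practitioners".
- **The nine IPE question blocks, from Fidelity & Adaptation to Unintended Outcomes:** each lists "Systemic practitioner analysis of case files" among its intervention-group methods.
- **Analysis of keyworker casefiles:** this section sets out the purpose, sampling, criteria and coding. It says "The evaluation team will then use the assessment criteria to code and analyse case files to understand if there has been changes to practice". Systemic Practitioners appear here only in the feasibility step: "We will work with intervention area systemic practitioners and team managers to assess whether it is feasible in terms of capacity and capability of". The sentence breaks off at that point, so whose capacity is meant is not stated.

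The same section gives the purpose ("Observing practice through analysis of keyworker casefiles could be a way of assessing change") and the sample. For the earlier period, each intervention area is asked for "three randomly selected cases from families who closed to the service just before the pilot began". For the later period, it is asked for "three files from cases who closed in the latter stages of the pilot". The files are anonymised and limited to information on practice and process. Masking of the period is not mentioned. Table 12 and the list that precedes it describe the casefile analysis without naming an assessor.

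**The concern.** The two assignments are not equivalent. According to the sections Systemic practice pilot and Local authority systemic practitioners, these staff are employed to embed the model. They run the monthly group reflective sessions, consult one-to-one with keyworkers and support the use of systemic tools. If they also judge the files, they judge the product of their own work.

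The Protocol recognises this hazard elsewhere. Under Randomisation and blinding, it chooses self-reported measures and routine data for family outcomes so that unblinded keyworkers do not introduce observer bias. That statement covers family outcomes only, but the reasoning carries over.

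The casefile section describes understanding whether practice has changed as a key part of the IPE. The casefile analysis is listed under every IPE question, and Table 12 links it to practice quality, family functioning, therapeutic alliance and mental wellbeing. Feasibility for a full-scale trial states that IPE findings contribute to the feasibility judgement. An assessor's expectation of improvement could therefore enter that evidence as an observed change in practice.

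**Working it through.** The Protocol gives no figure to reproduce for this component. The check is a comparison of the text plus a file count.

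**1. Who codes the files?**

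| Place in the Protocol | Assessor named |
|---|---|
| Nine IPE question blocks | Systemic Practitioner |
| IPE research methods, item 6 | Embedded Systemic Practitioners, if feasible |
| Analysis of keyworker casefiles | Evaluation team |
| Table 12 and the list before it | None |

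All of this is current text, and no sentence gives one version precedence. The practitioner version appears ten times (nine blocks plus item 6), so it is not a single slip. The evaluation-team version appears once, in the section that specifies the method.

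**2. How many files?**

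- Pre-pilot: 6 intervention areas x 3 = 18.
- Late-pilot: 6 x 3 = 18.
- Total: 18 + 18 = 36.
- Control areas: 0. The request goes to intervention areas only, and the control-area IPE list contains no casefile item.

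**3. What protects the comparison?**

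- *Control files:* none, so an assessor's tendency to read late files more favourably cannot be separated from real change.
- *Anonymisation:* it removes identities. It is not stated to remove dates or other signs of period.
- *Analyst blinding:* under Randomisation and blinding, this concerns trial arm in the main analytical dataset. All case files come from one arm, so it gives no protection here.

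**4. What does each version imply?**

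- *Systemic Practitioners code:* the assessor delivers the model, and nothing hides the period.
- *Evaluation team codes:* the assessor does not deliver training or reflective practice in the areas, but nothing is said to hide the period from them either. This version removes the self-rating problem and leaves the masking question open.

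**5. What kind of analysis is planned?** The text after Table 12 places case files in the qualitative strand, under reflexive thematic analysis. No numeric score, standard deviation or significance test is specified.

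**The case against.** The strongest reply is that the dedicated section should govern. It is the only place that gives sampling, criteria, timing and coder, and it names the evaluation team. On that reading the other entries are loose labels and delivery staff rate nothing. This is a fair guess at intent, but the Protocol does not say it. Ten entries say otherwise, and a local authority that followed them would be following the Protocol.

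The second reply concerns weight, and it stands. The component depends on a feasibility assessment. It is one of six or seven sources under each IPE question and is to be triangulated with the others. It is neither the primary outcome nor one of the six secondary outcomes: practice quality as a trial outcome comes from the keyworker survey in both arms (Table 9). It is not named in the fidelity measures of Table 10 or the progression criteria of Table 13.

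Three stronger readings are tempting, and the document does not support them.

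- *A reader might treat the 18 v 18 files as a two-sample test and attach a false-positive rate to an assumed rater shift.* No score or test is planned, no size of shift can be taken from the Protocol, and files within an area would not be independent.
- *A reader might infer that the trial's effect estimate is biased.* The case files do not enter it.
- *A reader might infer that the case files are the only evidence of practice change.* They are the only planned before-and-after source drawn from practice records, but the survey and the observations with an adapted coding tool also address practice.

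A last reply is that masking may fail, because the content being coded is systemic principles, terms and tools. That is true. It limits what masking can achieve, but removing dates and mixing the order still removes the most obvious cues.

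**Conclusion.** The contradiction is real, and the Protocol does not resolve it. Under the version in the nine IPE question blocks and item 6, staff who deliver the model would judge its uptake, with no concealment of period, in an uncontrolled comparison of 18 pre-pilot and 18 late-pilot files. The consequence is confined to the IPE: assessor expectation may be read as practice change. The RCT estimate, the sample size and the progression thresholds are unaffected. The size of any bias cannot be stated from the document.

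The conclusion assumes that the casefile analysis proves feasible and goes ahead. It also assumes that assessors would know or could tell the period of a file, since nothing planned prevents this. The point deserves correction rather than mere tidying, because the choice of assessor decides whether this evidence is independent of delivery.

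**What to change.** Amend the nine IPE question blocks and item 6 of IPE research methods to match Analysis of keyworker casefiles: the evaluation team codes all files. Limit the Systemic Practitioners' role to helping judge feasibility and extracting the selected files.

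As an inexpensive addition, state in the casefile section that:

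- dates and explicit period markers are removed where possible during the anonymisation already planned;
- pre-pilot and late-pilot files are mixed and coded in random order;
- the period code is held back until coding is finished;
- the report acknowledges that systemic terms or tools in late files may still reveal the period.

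The cost is a wording change in ten places, plus redaction and shuffling of 36 files that are being anonymised anyway. No additional data collection is needed.

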Systemic Psychotherapist Delivery Lead

The Systemic Psychotherapist Delivery Lead hired by IFT will take a leading role in the delivery of training in local authorities and supporting local authority systemic practitioners to embed systemic practice working to ensure fidelity and consistency

⁴³ AFT. Training route for family and systemic psychotherapy and development of systemic. Available at: practice <https://www.aft.org.uk/page/routestogqualification>

across local authorities including overseeing the systemic practice virtual hub. They will provide clinical supervision to local authority systemic practitioners.

Systemic training to keyworker teams

A core component of embedding of systemic practice will be the delivery of high-quality systemic training to local authorities. Training will be mandatory for keyworkers and will be led by IFT's Systemic Psychotherapist Delivery Lead and a number of qualified IFT tutors to ensure consistency. Local authority systemic practitioners will attend and support the training. The training will include:

5 days of CPD certified systemic training course mandatory for all keyworkers. It is envisaged that training will take place fortnightly for 10 weeks to ensure practitioners are not overloaded, allowing them time to reflect and test learning in everyday practice, and take this back to subsequent training to accumulate knowledge.

Based on evidence from training and implementation of systemic practice, many local authorities have struggled to ensure all staff undertake the full 15 days of foundation level training. This is due to limited capacity across keyworker teams, and differing levels of skills, academic aptitude and motivation from practitioners leading to high dropout rates. Instead, the full 15 days of foundation level training will be offered to a smaller group of keyworkers ('systemic champions' as set out below).

The aims of the 5 days of training will be to:

- Introduce underlying theories, principles and evidence base for systemic practice.
- Provide an overview and framework of different approaches and models of systemic family therapy.
- Introduce systemic tools and measures for keyworkers to develop their practice.
- Introduce ways for keyworkers to develop their own self-reflective practice.

An overview of the course themes and learning objectives are set out below.

- Theme 1: Overview of Systemic Ideas
 - Understand basic systemic theories.

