The hub will also include dedicated forums which will include a main forum for all those within the pilot for general Q&A and networking between the intervention local authorities. It will also include forums for each local authorities' keyworkers, in addition to a private forum for the six hired Systemic Practitioners to communicate across the intervention local authorities.

Local authority Systemic Champions

Evidence suggests that practitioners acting as systemic champions or advocates who can promote and model best practice can play a key part in embedding systemic practice in local authorities.⁴⁴ Around a 10-20 percent of keyworkers per local authority will be chosen to be 'systemic champions' and receive an additional 10 days of training over the course of the pilot (above the 5 days of systemic training for all keyworkers). This will

⁴⁴ Sebba, J., Luke, N., McNeish, D., Rees, A. (2017). Children's Social Care Innovation Programme: Final evaluation report. Oxford: Rees Centre, University of Oxford.

provide an equivalent of a Foundation Course in Systemic Practice.⁴⁵ They will support local authority systemic practitioners to embed practice throughout keyworker teams with the aim of having at least one systemic champion within each keyworker team or locality. They will help with trouble shooting, identifying barriers and supporting enabling factors. It is envisaged that systemic champions could have a specific theme within systemic practice in each local authority that they focus on (such as working with difference across cultures, self-reflexivity, life-cycle development). It is hoped they will be a critical factor in the sustainability of systemic work after the pilot.

Systemic group reflective practice

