The survey will take a census approach where keyworkers will be sent a direct link and promoted by keyworker managers. The online surveys will be created using Ecory's bespoke survey platform and tested in-house, with Coram and IFT as well as with local authorities before going live. The control group baseline and endline surveys will be designed to last no more than 10 minutes, and the intervention group baseline, post-training and endline survey will be designed to last no more than 15 minutes.

To maximise survey response rate, keyworkers will be sent links directly to their email addresses by Ecorys. The survey will also be promoted through multiple routes. For keyworkers in the intervention arm, keyworkers will be asked to complete the pre-survey and post-survey as part of the training sessions. Time for completion will be built into the introductory day and final training sessions. For keyworkers in the control, it will be mandatory for keyworkers to complete the survey as part of their online training on outcome measures for families.

In control and intervention local authorities, the endline survey will be promoted by the systemic practitioner and keyworker managers. Baseline, midline (for intervention) and endline surveys will be matched via keyworker emails. A targeted reminder strategy using their emails will be implemented using behavioural insights to design attractive materials, and targeted telephone reminders will be used if certain teams have a low response rate. It is hoped that a high response rate will be achieved given Foundation's pilot evaluation in Rotherham received a 96% response rate at baseline and 85% at

endline.⁹² However, the number of keyworkers will be much higher and therefore the response rate will likely be lower than in the Rotherham study.

Keyworker focus groups and interviews

As part of the IPE, semi-structured focus groups and interviews will take place with keyworkers (including systemic champions) in both intervention and control local authorities. Interviews will also be conducted with embedded systemic practitioners and senior staff, such as service leads and team managers. Interviews and focus groups will focus on key aspects of implementation, delivery, and perceived impact.

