Confidentiality would only be broken if there was a risk of harm. Participants will be anonymous in all outputs. Any safeguarding issues that arise will be escalated in

accordance with our safeguarding policies. Appropriate signposting and referral mechanisms will be in place for if children/young people or parents/carers disclose anything where there is a legal obligation to act on. It will be made clear in data privacy notices and any information shared with participants what may happen if they do disclose anything that would warrant a safeguarding consent.

We will ensure participants receive good quality, accessible information about our research to support informed consent, making it clear that participation is voluntary. We will provide and support the use of accessible evaluation materials such as information sheets, FAQs, and consent forms, using plain, simple language and pictures where appropriate. We will seek consent to take part in the evaluation, surveys and interviews from children/young people and from parents/carers.

For primary data collection (i.e. interviews) we will make it clear to participants that they will not have to answer questions they do not want to, and that they could stop the interview at any time. We will also have a list of resources for support to hand to participants if we feel it appropriate.

Registration of the trial will be undertaken by the Department for Education via the Cabinet Office's evaluation taskforce registry.

Equity, diversity and inclusion

We are committed to creating equitable and inclusive research. We have strict ethical protocols and processes in place, and Coram's research ethics framework requires us to do our research in an accessible and inclusive way. Our policies go beyond legal requirements, aiming to involve people from underrepresented communities. We are upfront about the drawbacks of being a predominantly White team in our research, and recognise this will inevitably affect our work (and take action to address this in our recruitment practices).

We understand the power imbalance that research with vulnerable children/young people and their families can bring. We will apply reflexivity to our research to understand how we may influence and interpret findings and report this honestly. We will consider racial diversity and inclusion prominently in our evaluation plans and ongoing work with local authorities as well as DfE and within the pilot such as IFT and Ecorys.

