Throughout the pilot, we will focus on encouraging inclusivity and meaningful participation by:

- minimising the burden on research participants by ensuring questionnaires and interview discussions are focussed on the most pertinent questions
- working flexibly to meet the varied needs and preferences of different participants and to reduce barriers to participation, including carrying out interviews at times to suit participants, and using creative, child-friendly, easy-read and/or translated tools and methods where appropriate
- using accessible information sheets and consent forms and checking for informed consent throughout
- confirming with participants prior to any interviews whether they have any support or access needs (e.g. being accompanied by a trusted person, having the interview over two shorter sessions, easy read formats, interpreters etc.)
- research activities will take place in safe, culturally-appropriate, accessible settings
- signposting to additional support if needed.

Data protection

Maintaining data security is a key risk mitigation for the pilot and we will work closely with local authorities to ensure data is collected, shared, analysed and stored appropriately.

Coram and Ecorys holds a Cyber Essentials Plus certificate. All Coram and Ecorys staff receive data security and GDPR training.

Coram and DfE both completed a Data Protection Impact Assessment (DPIA) for the pilot. In line with these DPIAs, data for the purposes of this research study will be collected under these lawful bases:

- **Personal data** will be processed under the basis of **Public Task** under UK General Data Protection Regulation Article 6.1(e).
- **Special category personal data** being processed for research purposes is under GDPR Article 9.2(j) and DPA18 Schedule 1 Part 1.4(a), (b)&(c) for special category data including data considered to be a protected characteristic under the UK Equality Act 2010.

For ethical reasons Coram and Ecorys will actively request consent from those providing data as part of the evaluation (for example, Family Outcome Questionnaire, keyworker survey and interviews).

The pilot will also be informed by the Department for Education's Personal information charter.⁹⁹

Coram and each of the local authorities will be the **joint controllers** of personal data throughout the pilot. Coram and the local authorities will make decisions together about what data will be collected and how they will be processed for the evaluation.

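### The baseline keyworker survey is mandatory for control staff but only requested of intervention staff, against the protocol's own consent terms, and the endline survey is to be promoted in both arms by a post that only intervention authorities have.

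*Protocol*

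**What the plan says.** The protocol's Practitioner surveys section sets the completion rules. For control keyworkers at the start of the pilot, "it will be mandatory for keyworkers to complete the survey as part of their online training on outcome measures for families". For intervention keyworkers, "keyworkers will be asked to complete the pre-survey and post-survey as part of the training sessions", and "Time for completion will be built into the introductory day and final training sessions". The intervention training is itself compulsory: under Systemic training to keyworker teams, "Training will be mandatory for keyworkers".

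The Ethics section commits the team to clear information for participants, "making it clear that participation is voluntary". The Data protection section says that the two evaluation organisations "will actively request consent from those providing data as part of the evaluation" and gives the keyworker survey as one of its examples.

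For endline, Practitioner surveys says of control and intervention authorities together that "the endline survey will be promoted by the systemic practitioner and keyworker managers". The Systemic Practice Virtual Hub section describes a "private forum for the six hired Systemic Practitioners", for contact across the intervention authorities. The section on local authority systemic practitioners likewise places the post in intervention authorities.

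**The concern.** There are two separate faults.

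First, a survey cannot be compulsory in one section and subject to a consent request in another. The rule also differs by arm, and no reason is given for compelling one arm and asking the other.

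Second, one of the two named endline promoters does not exist in the control arm. In the intervention arm, that promoter has a stake in the answers. The intervention survey covers the local systemic lead's support, group reflective supervision and the use of systemic tools, and the systemic practitioner runs the reflective sessions and supports use of the tools.

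The survey is the only quantitative source for secondary research questions 5 and 6, professional wellbeing and practice quality. Both are self-reported on adapted question sets, and the protocol says that no validated measure of practice quality was found. If prompting differs by arm, the endline comparison can be distorted in two ways: different kinds of keyworker may reply in each arm, and intervention keyworkers may answer more favourably because the person asking is the one whose work is being judged.

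**Working it through.** The protocol states no figure on this point, so the check sets the sections side by side.

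**Which wave the compulsory wording covers.** It is tied to the control arm's online training in the family outcome measures. Tables 8 and 9 place that training at the start of the pilot, and Table 11 gives control authorities a baseline and an endline survey only. The wording therefore governs the control baseline survey. Nothing makes the endline survey compulsory in either arm.

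**Consent.**

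| Section | Statement | Who it covers |
|---|---|---|
| Practitioner surveys | Completion mandatory | Control keyworkers, baseline |
| Practitioner surveys | Completion requested, in session time | Intervention keyworkers, pre- and post-training |
| Data protection | Consent requested; keyworker survey named | Both arms |
| Ethics | Participation voluntary | Participants in general |

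The clearest conflict is between the first and third rows. The Ethics statement supports it, but the sentence there on seeking consent for surveys names only children, young people, parents and carers.

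**Endline promoters by arm.**

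| | Intervention | Control |
|---|---|---|
| Local authorities | 6 | 4 |
| Systemic practitioners hired | 6 | 0 |
| Named endline promoters available | 2 of 2 | 1 of 2 (managers only) |

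The control package under Incentives for control local authorities contains no such post, and the exclusion criteria rule out authorities that had hired or commissioned clinicians to support keyworkers in the last three years. The same slip appears under Recruitment, where keyworkers in both arms are told to expect support from their own authority's systemic practitioner.

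**What a size would need.** Let r_I and r_C be the endline response proportions, and let d be the mean outcome of responders minus that of non-responders, taken as equal in both arms. Each arm's observed mean is shifted by (1 − r)d, so the intervention-minus-control difference is shifted by (1 − r_I)d − (1 − r_C)d = −d(r_I − r_C). The protocol supplies none of r_I, r_C or d. It quotes 96% at baseline and 85% at endline from one earlier study, not split by arm, and expects lower response here. Favourable answering would add a further term, also unknown.

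**Whether the plan would reveal an imbalance.** Progression criterion 5 in Table 13 is green at 200 or more follow-up measures in total. It is not split by arm, so a lopsided response could still pass.

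**The case against.** The strongest reply is that these are drafting slips with little practical effect. Much of it stands. At baseline both arms complete the survey around a training session, and intervention attendance is mandatory with time set aside, so the real gap in baseline response may be small. At endline, emailed links from the survey contractor, keyworker managers, targeted email reminders and telephone calls to low-responding teams all reach control staff. Baseline scores are collected for both outcomes and matched to endline by email, the Analysis section plans a missing-data assessment, and these are two of six secondary outcomes in a pilot.

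The reply does not remove the conflict over consent or the fact that one promoter is present in one arm only. Baseline adjustment can reduce selection that is related to baseline scores; it cannot undo favourable answering at endline.

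A reader might infer four stronger points, and the protocol supports none of them:

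- **The mandatory rule biases the endline difference.** It applies to the control baseline only.
- **Control baseline data could not be used.** The Data protection section relies on Public Task as the lawful basis and seeks consent for ethical reasons. Nothing says that responses would be excluded.
- **Control authorities have no endline promotion.** It is weaker there by one route, not absent.
- **The bias can be given a value in standard deviations.** Any such value would rest on response rates and a responder gap that the protocol does not contain.

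**Conclusion.** Both faults hold. The completion rule for the baseline keyworker survey differs by arm and, in the control arm, contradicts the Data protection section and the general voluntariness statement under Ethics. Endline promotion cannot be carried out as written in any of the four control authorities. In the six intervention authorities it would involve the person who delivers the support being rated.

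The consequence is a risk of differential response and of favourable answering on two self-reported between-arm outcomes. Its direction and size cannot be established from the protocol. The conclusion assumes only that the promotion sentence would be followed as written and that control authorities do not acquire a systemic practitioner during the trial. It is a modest point for secondary outcomes in a pilot, worth correcting because the remedy is cheap and most of it is already planned.

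**What to change.** 1. Remove the systemic practitioner from endline survey promotion. Use the same routes in both arms: contractor emails and reminders on one schedule, plus keyworker managers. Correct the matching sentence under Recruitment.
2. Replace the mandatory wording with one consent-based completion rule for both arms, consistent with Ethics and Data protection. State whether consent was in fact sought from control keyworkers at baseline.
3. Report keyworker survey response by arm and by local authority at baseline and endline. The Analysis section already promises participant flow and outcome completion rates, so this adds the breakdown by authority.

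The cost is wording, one reminder schedule and one table. Endline response in the intervention arm may fall slightly without the extra promoter. Annex A dates the pre-training survey November 2024 to April 2025, so the baseline rule may be correctable only in reporting. The endline survey is scheduled for April to May 2026, and its promotion route can be changed if the correction is made before then.
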